## SYNOPSIS

Title	Treatment of High-Risk Prostate Cancer Guided by Novel Diagnostic Radio- and Molecular Tracers (THUNDER): A Two-part Phase 2/ 3 Trial	
Protocol Number	CTO21042GZA	
Phase	Phase 2/ Phase 3	
Study Sites	The study will be conducted at multiple centers across Europe.	
Study Objectives and Endpoints		
Tier	Objectives	Endpoints
Primary:		
Phase 3 – Intensification Study High-risk prostate cancer (PCa) and positive prostate-specific membrane antigen (PSMA) positron emission tomography (PET)/ computed tomography (CT) and/or Decipher high (> 0.6) patients	To determine improvements in PSMA PET/ CT metastasis-free survival (ppMFS), where ppMFS is defined as the time from randomization to the date of detection of at least 1 new PSMA-PET-positive distant lesion as compared to baseline or date of death from any cause.	Incidence of ppMFS over time. PSMA PET metastatic progression is defined as the appearance of at least 1 new PSMA-PET-positive distant lesion compared with the baseline scan.
Phase 2 – De-intensification Study High-risk PCa and negative PSMA PET/ CT for regional and distant metastases and low/ intermediate Decipher ( $\leq 0.6$ ) patients	To determine improvements in Quality of Life indices and effectiveness of up to 96 weeks (24 months) of darolutamide plus standard of care (SOC) radiotherapy (RT) as compared to standard treatment (24 months androgen deprivation therapy [ADT; i.e. luteinizing hormone releasing hormone (ant)-agonists (LHRHA)] plus SOC RT) or standard treatment with ADT plus darolutamide.	Health related Quality of Life (HRQL) will be reported by subjects using the Expanded Prostate Cancer Index Composite (EPIC) questionnaire. A clinically important point reduction in EPIC subdomain score is defined as follows: sexual (11 points), and hormonal (5 points) as detected at 12 months. EPIC scores will be measured on a yearly basis to monitor late effects.
Secondary:		
Applies to Phase 3 and Phase 2	Overall survival (OS)	The following secondary endpoints will be evaluated on the basis of time to the event: 
 
OS will be measured from the date of randomization to the date of death or last known follow-up date, with patients alive at the last known follow-up time treated as censored
 

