

Study Oversight
	
The study will be subject to oversight by an independent data monitoring committee (IDMC) comprised of at least 3, independent members (i.e., external to the study team and Sponsor), including a chairperson and at least 2 further members with clinical or statistical expertise (at least one member must be a statistician).
 
The IDMC will convene to actively monitor and review the cumulative safety and efficacy data for the ongoing study and can make recommendations about early study closure or changes to the conduct of the study. The Sponsor may decide to stop or make adaptations to the study based upon the IDMC recommendations.
 
Details of the membership function and governance of the IDMC for this study will be documented in a IDMC charter.

Number of Subjects
	
Total: Approximately 493 evaluable subjects will be concurrently screened and enrolled into the Phase 3 or Phase 2 study.
 
Phase 3: Approximately 360 evaluable patients determined to have high-risk localized or locally advanced PCa, with PSMA positive non-localized disease or a Decipher high score (> 0.6) will be enrolled to the Phase 3 study. Subjects with negative PSMA PET/ CT who subsequently return a high Decipher score will also be enrolled and randomized into the Phase 3 study. All Phase 3 subjects will be randomly assigned in a blinded fashion to receive darolutamide plus LHRHA, or darolutamide matched placebo plus LHRHA in a 1:1 ratio. All subjects will also receive primary SOC RT.
 
Phase 2: Approximately 133 evaluable patients determined to have localized PCa by PSMA PET/ CT (PSMA negative for regional or distant metastases) with a low/ intermediate Decipher test score (<math>\leq 0.6</math>) will enter the non-randomized, Phase 2, single treatment arm, de-intensification study. All Phase 2 study subjects will be allocated to receive darolutamide and primary SOC RT.

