	
Decipher score
 
 
a. Subjects who have a negative PSMA PET/ CT and a tumor with a low/ intermediate Decipher score (<math>\leq 0.6</math>) will be eligible to enter the non-randomized Phase 2 study.
 
b. Subjects who have a negative PSMA PET/ CT and a tumor with a high Decipher score (<math>> 0.6</math>) will be eligible to be randomized to either arm of the Phase 3 study.
 
c. In subjects with positive PSMA PET/ CT, the Decipher score will not determine the treatment allocation.
 
 
 
6. Willingness to undergo SOC RT and long-term ADT (treatment with darolutamide and/ or LHRHA)
 
7. Subject is able and willing to provide written informed consent, which includes compliance with and ability to undergo all study procedures and attend the scheduled follow-up visit/s per protocol.
 
8. Subject must be over 18 years of age.
 
9. Subject able to swallow whole study drug tablets.
 
10. To avoid risk of drug exposure through the ejaculate (even men with vasectomies), subjects must use a condom during sexual activity while on study drug and for 3 months after the last administration of study treatment. Donation of sperm is not allowed during the treatment phase and for 3 months after the last administration of study treatment.
 
11. Adequate organ function determined by the following local laboratory values:             
 
a. Adequate bone marrow function: Hemoglobin <math>\geq 100</math> g/L, white cell count (WCC) <math>\geq 4.0 \times 10^9/L</math>, absolute neutrophil count (ANC) <math>\geq 1.5 \times 10^9/L</math> and platelets <math>> 100 \times 10^9/L</math>
 
b. Adequate renal function: calculated creatinine clearance <math>> 30</math> mL/min (Cockcroft-Gault)
 
c. Adequate liver function: alanine aminotransferase (ALT) <math>< 2</math> x upper limit of normal (ULN) and total bilirubin <math>< 1.5</math> x ULN, (or if total bilirubin is between 1.5 to 2 x ULN, they must have a normal conjugated bilirubin)
 
d. Testosterone levels <math>> 50</math> ng/dL
 
 
 
 
Exclusion criteria: A subject who meets any of the following criteria must be excluded from the study:
 
 
1. Definitive radiologic evidence of metastatic disease outside of the pelvic nodes (M1a, M1b or M1c) on conventional imaging (i.e., bone scan, CT scan, MRI)
 
2. PCa with predominant non-adenocarcinoma features (sarcomatoid or spindle or neuroendocrine small cell or squamous cell components or other non-adenocarcinoma)
 
3. Prior pelvic radiotherapy
 
4. Contraindications for pelvic radiotherapy
 
5. Contraindications for ADT (treatment with darolutamide and/ or LHRHA)
 
6. Contraindications or known allergy to PSMA PET/ CT tracers.
 
7. Prior local therapy for PCa (e.g., radical prostatectomy, high-intensity focused ultrasound [HIFU], cryotherapy). Subjects with previous transurethral resection of the prostate (TURP) or Millin prostatectomy are eligible for participation
 
8. Prior systemic therapy for PCa, except for patients with a positive PSMA PET/ CT staging who are allowed to start with ADT if no more than 4 weeks prior to randomization.
 

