
Intervention
	
Darolutamide and Matching Placebo
 
Study subjects allocated to receive darolutamide or matching placebo (as applicable, per study phase) will be administered the study drug as 600 mg (2 x 300mg tablets) orally twice daily for up to 96 weeks (24 months).
 
Subjects will be instructed to take tablets whole with food. If a dose is missed, the dose should be taken as soon as the subject remembers within 6 hours of the missed dose. If delayed by more than 6 hours, the missed dose should be omitted. The subject should not take 2 doses together to make up for a missed dose.
 
Subjects will receive 3 bottles of their assigned treatment at time of treatment allocation for three 28-day cycles. The first administration should occur within 14 days after treatment allocation. Following evaluation at week 12 (3 months), subjects will receive a second allocation of 3 bottles of study drug for another three 28-day cycles. These 12-week cycles are continued until determination of the primary endpoint (ppMFS) or until the maximum treatment period of up to 96 weeks (24 months).
 
Darolutamide and matching placebo will be manufactured and provided by Bayer Inc.
 
Luteinizing Hormone Releasing Hormone (Ant)-agonists
 
The choice of LHRHA is to occur at the discretion of the treating clinician. Administration of the LHRHA should be according to the product information guide. Options include, but are not restricted to, goserelin, leuprorelin, triptorelin and degarelix.
 
PSMA PET Tracer
 
All PSMA PET scans are considered as standard of care in analogy with the 2022 NCCN guidelines. All PET tracer are allowed. Patients that have undergone a PSMA PET-CT prior to entering the trial, that is not older than 3 months, are eligible to enter the trial. These patients do not need to undergo a new PSMA PET-CT.
 
Radiation Standard of Care
 
The current protocol will be as pragmatic as possible and allow multiple approved RT schedules. These schedules are applicable to all arms in the study. The RT field will be prostate only in case the risk of lymph node metastases is less than 20% as per Roach nomogram or include the whole pelvis in case the risk is > 20% even if the PSMA PET/ CT does not show pelvic nodal uptake. Patients with up to 5 M1 lesions on PSMA PET-CT, should receive SBRT to all lesions in both arms of the phase 3 trial. For delineation of the prostate, we suggest using the PACE C guidelines and for the lymph nodes the NRG guidelines (https://www.srobf.cz/downloads/nrg-oncology-updated-internati_.pdf).
 
More information in relation to RT details and regimens is provided in Appendix 4.

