	
number, we can extrapolate the number of patients needed to be screened as only 40% of patients will have a positive PSMA scan, based on the Australian ProPSMA study (Hofman 2020) and we hypothesize that 55% of patients with a negative PSMA PET would still have a Decipher high score.
 
The following assumptions apply:
 
Based on the data from randomized trials including high-risk PCa we estimate that the 5-year FFS is 70%. In 40% of cases, a PSMA PET will detect disease outside the prostate with approximately 20% having N1 disease and 20% M1 disease. In another 30% of cases, the PSMA will be negative, but the Decipher score will still be > 0.6. We expect that the patients with a positive PET outside the prostate have a higher failure rate with current standard treatment approaches with FFS of 60% and 40% for N1 and M1 disease, respectively, or 50% combined. We expect patients with a negative PET, but Decipher high score will have a FFS of 75%. From these data, it is estimated that the combined PSMA positive or Decipher high group has a 5 year FFS of 61%. We hypothesize an increase to 76% with the addition of darolutamide.
 
Assuming proportional hazards (and for the translation from number of events to number of patients also assuming exponential FFS), the calculations were made in Power Analysis and Sample Size (PASS) software and confirmed with simulations in R.
 
 
• Accrual: 3 years
 
• Additional follow-up: 3.5 years
 
• Total duration: 3 + 3.5 = 6.5 years
 
• 5 year FFS in control arm: 61 %
 
• 5 year FFS in experimental arm 76 %
 
• Hazard ratio: 0.56
 
• Two-sided alpha of 0.05
 
• Power of 80%
 
 
With these settings, the total number of events needed is 96. For this – assuming the proportion PSMA positive and Decipher high as presented before – an estimated 306 patients need to be enrolled. With an expected dropout of 15%, this results in a requirement for 493 patients in total to be screened. In simulations, the power of the trials proved to be robust against misspecification of the PSMA positive and Decipher high proportions in the screened population – when using the number-of-events-based stopping rule.
 
Phase 2:
 
The primary endpoint for this Phase 2 study will be to detect a clinically meaningful difference in the EPIC sexual and hormonal subdomain as detected at 12 months. A comparison will be made between the patients recruited in this single arm phase 2 trial with those recruited in the phase 3 trial. This will result in comparing patients receiving either darolutamide monotherapy versus standard of care ADT and ADT plus darolutamide. We aim to measure the scores on a yearly basis to monitor late effects. We expect the baseline quality of life at inclusion will be comparable for the phase 2 and phase 3 patients as they only differ in their PSMA PET-CT result and Decipher score. Consequently, only the treatment allocation influences the quality of life.
 
Assuming an 11 points difference in the sexual domain, a standard deviation of 31.1 (based on PROSTQA) and 10% dropout/ non-compliance/ consent withdrawal incorporated group sizes of 122 (Decipher low) and 153 (SOC) and 153 (SOC+darolutamide), the estimated power is 83% (based on a t-test assuming equal variances – as the primary analysis is an analysis of covariance (ANCOVA) with group and baseline score as predictors, this can be assumed a lower bound). This 11 point difference is considered as the threshold of a minimally important difference for the sexual domain.
 
Analysis of the Primary Endpoints

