--	---

	
Phase 3: ppMFS is defined as the time from randomization to the date of detection of at least 1 new PSMA-PET-positive distant lesion compared with the baseline scan or date of death from any cause. Event-free patients are censored at their last known follow-up date. ppMFS will be estimated using the Kaplan-Meier method. For the Phase 3 intensification study, the primary analysis comparing treatment arms will be a stratified log-rank test (stratified according to the randomization-strata).
 
Phase 2: EPIC mean changes in subdomain scores over time will be compared, both for change from baseline and absolute scores. The primary analysis will be an ANCOVA with group and baseline value as predictors. Given that at 1 year, the expected mortality is rather low, the primary analysis will treat deceased patients as having missing data under missing at random (MAR). As sensitivity analysis, the missing data for deceased will be imputed by worst score. An additional sensitivity analysis using trimmed means will be performed.

--	--

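### The Phase 2 EPIC comparison is non-randomised, yet the protocol rules out confounding by assertion and adjusts only for the baseline score

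*Protocol*

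**What the plan says.** The Protocol Synopsis (Number of Subjects) says that PSMA-negative patients with a Decipher score of 0.6 or less "will enter the non-randomized, Phase 2, single treatment arm, de-intensification study". Under Statistical Methods (Sample size rationale, Phase 2) it sets the contrast: "A comparison will be made between the patients recruited in this single arm phase 2 trial with those recruited in the phase 3 trial". Comparable baseline quality of life is expected "as they only differ in their PSMA PET-CT result and Decipher score", and the text then concludes: "Consequently, only the treatment allocation influences the quality of life".

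Analysis of the Primary Endpoints (Phase 2) fixes the model: "The primary analysis will be an ANCOVA with group and baseline value as predictors". The two sensitivity analyses named there are worst-score imputation for deceased patients and trimmed means.

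The Phase 2 primary objective goes beyond quality of life: "To determine improvements in Quality of Life indices and effectiveness of up to 96 weeks (24 months) of darolutamide plus standard of care (SOC) radiotherapy", as compared with standard treatment or with ADT plus darolutamide.

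**The concern.** The inference does not follow. Similar EPIC scores at baseline do not guarantee a similar course to 12 months under the same treatment, and the two features said to be the only differences are the ones the trial uses to separate patients by risk. If anything besides treatment moves the 12-month score differently in the two cohorts, the ANCOVA group coefficient will report it as a treatment effect. Neither sensitivity analysis addresses this: one concerns deaths, the other outlying scores.

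The plan is also uneven. The randomised Phase 3 comparison is stratified for number of high-risk features, PSMA status, Decipher, early ADT start and site. The non-randomised comparison, which has more need of adjustment, gets one covariate. At stake is the primary claim of the de-intensification study: that darolutamide without LHRHA preserves sexual and hormonal quality of life better than standard treatment.

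**Working it through.** **The premise against the protocol's other rules (all in the Synopsis)**

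- *Cohort definition.* Phase 2 is PSMA-negative with Decipher of 0.6 or less; Phase 3 is everyone else. No Phase 3 patient matches a Phase 2 patient on both features. On the planning figures, 40/70 = 57% of Phase 3 is PSMA-positive and 30/70 = 43% is PSMA-negative with high Decipher.
- *ADT before baseline.* Exclusion criterion 8 reads "Prior systemic therapy for PCa, except for patients with a positive PSMA PET/ CT staging who are allowed to start with ADT", within 4 weeks of randomisation. Such patients exist only in Phase 3, where early ADT start is a stratification factor. If their baseline EPIC is taken after ADT has begun, the one adjusting covariate already carries a treatment effect.
- *Blinding.* Phase 3 is placebo-controlled and blinded. Phase 2 is a single arm in which all patients are allocated darolutamide, so they know what they take. EPIC is patient-reported.

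**The plan's own power figure**

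Inputs from Sample size rationale, Phase 2: difference 11, SD 31.1, groups of 122 and 153. Two-sided alpha of 0.05 is listed under Phase 3 and assumed here.

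- SE = 31.1 × √(1/122 + 1/153) = 3.77 points.
- 11/3.77 = 2.91, and Φ(2.91 − 1.96) = 83.0% (82.7% with the noncentral t).

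The stated 83% reproduces, so the problem is bias and not arithmetic.

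**Illustration of bias**

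Let b be a residual cohort difference that baseline EPIC does not remove. The documents give no value, so the range is assumed. With no true treatment effect, the chance of a significant result in favour of Phase 2 is 1 − Φ(1.96 − b/3.77).

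| Assumed b (points) | Chance of a false claim of benefit |
|---|---|
| 0 | 2.5% |
| 3 | 12% |
| 4 | 18% |
| 5 | 26% |

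In the other direction, with a true effect of 11 and an opposing bias of 3, power is Φ(8/3.77 − 1.96), about 56%.

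**Direction**

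The mechanisms do not all point the same way. Unblinded reporting could inflate a benefit. A comparator baseline lowered by ADT would tend to mask one, because the comparator then appears to decline less. With assumed values (a 15-point drop in 30% of comparators, baseline correlation 0.5), the shift is about −0.5 × 0.30 × 15 = −2.25 points.

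**Restricting the comparator to PSMA-negative, Decipher-high patients**

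153 × 30/70 = 66 per arm. SE = 31.1 × √(1/122 + 1/66) = 4.75, and power for 11 points is about 63%. These patients cannot have started ADT early, but all have Decipher above 0.6 against 0.6 or less in Phase 2.

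**Effectiveness**

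The planning rates are 5-year FFS of 70% overall, 50% for PSMA-positive and 75% for PSMA-negative, Decipher-high patients. They imply for the remainder (70 − 0.40 × 50 − 0.30 × 75)/0.30 = 91.7%. If the high-Decipher share is taken as 0.60 × 0.55 = 33%, the figure is (70 − 0.40 × 50 − 0.33 × 75)/0.27 = 93.5%. Phase 3 controls are put at 61%. The cohorts are therefore planned to differ widely in outcome before any treatment effect.

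**The case against.** The protocol calls Phase 2 non-randomised repeatedly and hides nothing. Baseline adjustment does deal with cohort differences already visible in baseline EPIC. Visit schedules are the same in both parts. Methods are to be elaborated in an SAP, where further covariates and subgroup comparisons often sit. These points lower the severity, but they do not answer the concern: the protocol states the causal premise outright and fixes the primary model, so this is not a detail left open.

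Stronger readings are tempting and should be resisted.

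- *Radiotherapy.* A reader might infer that Phase 2 scores better because it gets less radiotherapy, given "Patients with up to 5 M1 lesions on PSMA PET-CT, should receive SBRT to all lesions in both arms of the phase 3 trial". But the prostate and pelvic schedules apply to all arms, the field follows nodal risk even without PSMA uptake, and nothing in the document links SBRT of distant lesions to EPIC sexual or hormonal scores.
- *Early ADT.* It might be taken to manufacture a benefit. In an ANCOVA it would tend to do the opposite, and the synopsis does not say when baseline EPIC is taken relative to ADT start.
- *Prognosis.* The FFS gap shows that the cohorts differ in outlook. It does not show that they differ in 12-month EPIC.
- *Effectiveness.* The objective's wording might suggest a planned primary oncological comparison. None exists: the Phase 2 primary endpoint is EPIC, and the cross-cohort FFS comparison is tertiary.
- *No value at all.* The comparison is not uninterpretable. It needs honest labelling and some checks.

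**Conclusion.** The concern holds, as a should-fix. The sentence that treatment alone influences quality of life is contradicted by the protocol's own rules on cohort definition, early ADT and blinding, and the primary model and its sensitivity analyses rest on it. The stated 83% power and the nominal error rate hold only if the residual cohort difference is zero. The figures of 12% to 26% and 56% show how sensitive the result is to differences well below the 11-point target. They rest on assumed biases of 3 to 5 points, SD 31.1, 122 and 153 analysed patients, and two-sided alpha of 0.05. They do not estimate the actual bias, whose size and net sign the document cannot give.

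**What to change.** 1. Delete the sentence and state that the Phase 2 contrast is non-randomised and open to residual confounding.
2. Add baseline factors already recorded, such as age and number of high-risk features, to the primary ANCOVA. PSMA status and Decipher category cannot both be adjusted away, because together they define the cohorts.
3. Prespecify two sensitivity analyses: one excluding comparator patients who started ADT before randomisation, and one restricting the comparator to PSMA-negative, Decipher-high Phase 3 patients. State that the latter still differ on Decipher and number about 66 per arm, with about 63% power.
4. Report Phase 2 oncological outcomes descriptively and make no claim of comparative effectiveness.

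The cost is wording and analysis only; treatment, sample size and procedures do not change. The model becomes slightly more complex. If the added covariates explained 10% to 30% of the variation in group membership and none of the outcome variance (assumed), power would fall from 82.7% to between 78.7% and 68.1%; covariates that predict EPIC would offset this. The sensitivity analyses are low-powered, and the share of early ADT starters is not given, so the size of the first cannot be stated. The final claim will be more modest.

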
Study Design
	
This Investigator-initiated, Treatment of High-Risk Prostate Cancer Guided by Novel Diagnostic Radio- and Molecular Tracers (THUNDER) study will be conducted in subjects with high-risk localized or locally advanced PCa. The study contains both a randomized Phase 3 treatment intensification study, and a treatment de-intensification non-randomized Phase 2 study. The aim of the THUNDER study is to improve the outcome of high-risk PCa by improved risk stratification using novel radiotracers (PSMA PET/CT) and a genomic classifier (Decipher) and subsequent treatment adaptation.
 
The hypothesis for the study is that treatment intensification based on a positive PSMA PET/ CT or Decipher high score (<math>> 0.6</math>) improves time to new metastases detected on PSMA PET/ CT in high-risk PCa.
 
In patients who are PSMA PET/ CT negative for regional or distant metastases with a low/ intermediate Decipher score (<math>\leq 0.6</math>), it is hypothesized that treatment de-intensification will improve patient quality of life while maintaining a good oncological outcome.
 
The study will be conducted at multiple centers across Europe.
 
Participation in the study will comprise a screening period, where the screening assessments must be completed before subjects are enrolled and randomized (if applicable). Eligible, consenting subjects will then undergo treatment according to their assigned study phase and treatment group, to occur over up to 96 weeks (24 months) with a post-treatment follow-up period to monitor safety and efficacy. The study will be closed 7 years from the time of randomization of the first subject.
 
The screening, treatment, and follow-up schedules are the same for both the Phase 3 and Phase 2 parts of the study, as delineated in the Schedule of Events (SOE).
 
Phase 3 Treatment Intensification Study: Patients with High-risk PCa and Positive PSMA PET/ CT and/ or Decipher high (<math>> 0.6</math>)
 
Approximately 360 evaluable patients with high-risk localized or locally advanced PCa, with PSMA positive non-localized disease or a Decipher high score (<math>> 0.6</math>) will be enrolled to the Phase 3 study. Subjects with negative PSMA PET/ CT who subsequently return a high Decipher score will also be enrolled and randomized into the Phase 3 study. All Phase 3 subjects will be randomly assigned in a 1:1 ratio to receive darolutamide plus LHRHA, or darolutamide matched placebo plus LHRHA, for up to 96 weeks (24 months). All Phase 3 subjects will also receive primary SOC RT. Subjects in Phase 3 should be commenced on an LHRHA and darolutamide or placebo within 14 days after randomization (unless started earlier) plus SOC RT for a period of approximately 1-8 weeks starting at 8–24 weeks after enrollment and randomization. Randomization of Phase 3 subjects will be stratified by 1 versus <math>> 1</math> high-risk features, N1 versus M1 PSMA positive versus PSMA negative disease, Decipher low/ intermediate versus high score, start of ADT within 4 weeks prior to randomization and clinical trial site.
 
Phase 2 Treatment De-intensification Study: Patients with High-risk PCa and Negative PSMA PET/ CT and Low/ Intermediate Decipher (<math>\leq 0.6</math>)
 
Approximately 133 evaluable patients determined to have localized PCa by PSMA PET/ CT (PSMA negative) with a low/ intermediate Decipher test score (<math>\leq 0.6</math>) will enter the non-randomized, Phase 2, single treatment arm, de-intensification study. As noted above, subjects with localized PCa by PSMA PET/ CT who return a high Decipher score (<math>> 0.6</math>) will be enrolled and randomized into the Phase 3 study. All Phase 2 study subjects will receive darolutamide for the study duration for up to 96 weeks (24 months) and primary SOC RT for a period of approximately 1-8 weeks starting at 8–24 weeks after enrollment.

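### The Phase 3 log-rank test is stratified by trial site as well as four clinical factors, so 96 events give less than the stated 80% power, by an amount that depends on the unstated number of sites

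*Protocol*

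**What the plan says.** Three parts of the protocol Synopsis bear on this.

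- **Analysis of the Primary Endpoints, Phase 3:** "the primary analysis comparing treatment arms will be a stratified log-rank test (stratified according to the randomization-strata".
- **Study Design, Phase 3:** five randomisation factors are listed. The list opens with "Randomization of Phase 3 subjects will be stratified by 1 versus" more than one high-risk feature. It continues with "N1 versus M1 PSMA positive versus PSMA negative disease" and ends with "Decipher low/ intermediate versus high score, start of ADT within 4 weeks prior to randomization and clinical trial site".
- **Sample size rationale, Phase 3:** for a hazard ratio of 0.56, two-sided alpha of 0.05 and 80% power, "With these settings, the total number of events needed is 96". This becomes 306 patients, and about 360 once 15% dropout is allowed for. Stratification is not mentioned.

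On sites the protocol says only: "The study will be conducted at multiple centers across Europe". Nothing in it exempts site from the analysis strata or provides for pooling sparse cells.

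**The concern.** Taken as written, the primary test is computed within every combination of site and the clinical factors. A stratified log-rank test compares arms only among patients at risk in the same stratum. If a stratum holds one or two patients, or all those still at risk are in one arm, an event there contributes to neither the numerator nor the variance.

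The trial stops on a count of events, and that count does not show how many of them are informative. The sponsor could wait the expected 7-8 years, collect all 96, and still have a test with materially less power than planned. A true hazard ratio of 0.56 could then be missed because of the choice of strata.

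**Working it through.** **1. Reproduce the plan's figure.** Inputs from the sample size rationale: 5-year rates of 61% and 76%, two-sided alpha 0.05, power 80%, 3 years' accrual plus 3.5 years' follow-up, 15% dropout.

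- Hazard ratio: ln(0.76)/ln(0.61) = 0.555, stated as 0.56.
- Freedman's formula for an unstratified log-rank test: (1.96 + 0.842)² × [(1 + 0.555)/(1 − 0.555)]² = 96 events. Schoenfeld's formula at 0.56 gives 94.
- Mean event probability with exponential survival and uniform accrual: 0.3135. Then 96/0.3135 = 306 patients, and 306/0.85 = 360.

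So 96, 306 and 360 all reproduce with no allowance for stratification.

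**2. Count the cells.** PSMA-negative patients enter Phase 3 only with a high Decipher score ("Subjects with negative PSMA PET/ CT who subsequently return a high Decipher score will also be enrolled and randomized into the Phase 3 study"). Exclusion criterion 8 bars prior systemic therapy "except for patients with a positive PSMA PET/ CT staging who are allowed to start with ADT", so PSMA-negative patients cannot have started ADT early.

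- N1: 2 (features) × 2 (Decipher) × 2 (early ADT) = 8 cells
- M1: likewise 8 cells
- PSMA negative: 2 (features) = 2 cells
- Total: 18 per site, so 180 cells at 10 sites and 360 at 20.

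With evenly spread factors and 306-360 patients, about 124-133 cells are occupied at 10 sites and 170-187 at 20. That is roughly 2-3 patients and fewer than one event per occupied cell.

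**3. Why events are lost.** At an event in a stratum with a and b patients at risk in the two arms, the expected count in the first arm is a/(a + b) and the variance is ab/(a + b)². If b = 0, the expected count is 1, observed minus expected is 0, and the variance is 0.

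**4. Simulated power.** Settings: N = 360, permuted blocks of 4 within cells, analysis at the 96th event, and the plan's own 5-year control rates of 60% (N1), 40% (M1) and 75% (PSMA negative). The effect is the plan's: a hazard ratio of 0.56 in every cell, or 0.545 in every cell, which gives 76% overall. The prevalences are assumptions. The even case has high-risk features 50/50 and, among PSMA-positive patients, Decipher high 55% and early ADT 50%. The skewed case has features 30/70, Decipher high 70% and early ADT 15%.

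| Sites (assumed) | Possible cells | Power, test as written |
|---|---|---|
| 3 | 54 | 75-80% |
| 5 | 90 | 71-75% |
| 10 | 180 | 62-72% |
| 20 | 360 | 49-58% |
| 30 | 540 | 38-51% |

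The same test without site gives about 76-82%, close to the unstratified test. Site as the only stratum costs just a few points, so the loss comes from crossing site with the other factors.

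Less favourable settings go lower. With N = 306 and even prevalences, under blocks or minimisation, power is 60-65% at 5 sites, 47-55% at 10 and 37-40% at 20.

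**5. Hand check.** Schoenfeld's approximation is power = Φ(½ × |ln 0.56| × √d − 1.96), where d is the number of informative events and |ln 0.56| = 0.580.

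- d = 96: Φ(2.84 − 1.96) = 81%
- d = 63 (simulated, 10 sites, even prevalences): Φ(2.30 − 1.96) = 63%
- d = 48 (simulated, 20 sites, even prevalences): Φ(2.01 − 1.96) = 52%

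The simulated powers in those two settings were 63% and 50%.

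**The case against.** **The size rests on inputs the protocol does not give.** The number of sites, the allocation method and block size, and the prevalence of high-risk features, of early ADT and of Decipher status among PSMA-positive patients are all missing. This stands. A reader might infer that the trial is in fact seriously underpowered, or that most of its events are wasted. The document does not support that as a flat statement: at 3 sites the loss is small and may be nil, and at 10 sites the prevalences alone move power by about 10 points. What does not depend on these inputs is the direction of the loss.

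**The SAP may settle it.** The Synopsis says methods will be further outlined there, and pooling rules often are. But the protocol has not left the strata open. It names the randomisation strata without qualification, so an SAP that dropped site would depart from the protocol's primary analysis.

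**The calculation was confirmed by simulation in R.** The protocol does not say which test those simulations used, so one cannot infer that they ignored stratification. What it reports is robustness to the PSMA-positive and Decipher-high proportions, which is a different question.

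**Analysing as randomised is an accepted principle.** That is right, and the test as written keeps its type I error. A reader who inferred an invalid test would be mistaken. The cost is in power only.

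**Decipher and early ADT need not go.** A reader might conclude that the test should keep only one or two prognostic factors. Removing site alone already restores nearly all the power, so cutting further is a matter of preference.

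**Conclusion.** The point holds as one of efficiency. The protocol fixes a primary test that crosses site with up to 18 clinical cells, while its 96 events are calculated as for an unstratified test. With 5 or more sites, every scenario run for the test as written fell short of 80%: about 71-75% at 5 sites, 62-72% at 10 and 49-58% at 20, on the assumptions listed. Only at about 3 sites is the shortfall slight (75-80%), and that would mean 360/3 = 120 Phase 3 patients per site in three years of accrual. The loss disappears almost entirely when site is taken out of the test. The number of sites and the factor prevalences are assumptions, so these figures are ranges and not an estimate for this trial. Because this is the only primary test of the Phase 3 part and the repair is cheap, it should be corrected before unblinding.

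**What to change.** In Analysis of the Primary Endpoints, Phase 3, replace the parenthesis tying the test to the randomisation strata with: *stratified by the randomisation factors except clinical trial site*. Add a rule, fixed before unblinding, for pooling clinical cells that turn out sparse. Keep site as a randomisation factor and bring it into a sensitivity analysis, for example a Cox model with site as a random effect. Carry the same wording into the SAP.

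Stratifying only by PSMA category and number of high-risk features (3 × 2 = 6 strata) would also be acceptable, but it is not required.

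The cost is one sentence plus the pooling rule, with no extra patients, events or follow-up. The small downside is that the primary test no longer conditions on site. The change should be made now, because altering the strata after unblinding would look data-driven.
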